10.2 Secondary Efficacy Endpoints

SALT I will also be analyzed as follows:

- Change from Baseline in SALT I at Week 24
- Proportion of subjects achieving a \geq 30% improvement from Baseline in SALT I at Week 24
- Proportion of subjects achieving a \geq 50% improvement from Baseline in SALT I at Week 24
- Proportion of subjects achieving a \geq 75% improvement from Baseline in SALT I at Week 24

Analysis of Secondary Efficacy Endpoints

The secondary endpoints will be analyzed using the FAS.

Main Analysis

The change from Baseline in SALT I at Week 24 will be summarized and analyzed as for the primary analysis of the primary efficacy endpoint (refer to Section 10.1).

For proportion-based secondary endpoints at Week 24, subjects with missing data for any reason will be imputed as described in Section 5.3. Frequency count and percentage of subjects achieving the criteria (and associated two-sided 95% Clopper-Pearson exact CIs) will be reported for each treatment group. The differences in proportion between each etrasimod treatment group and placebo, along associated two-sided 95% unconditional exact CIs, and p-value will also be reported. The proportion of subjects achieving the criteria in each etrasimod treatment group vs. placebo will be analyzed using a CMH test, adjusted for the randomization stratification factor SALT I score (< 50 , ≥ 50) at Baseline. Subjects in Cohort 1 will be considered in the ≥ 50 group as per inclusion criteria for Cohort 1.

Sensitivity Analysis

For the change from Baseline in SALT I at Week 24, the same sensitivity analyses as for the primary efficacy endpoint will be performed (refer to Section 10.1).

For the proportion-based secondary endpoints at Week 24, the following sensitivity analyses will be performed using imputed data or alternative analysis set:

- 1) **MI in FAS**: Missing response status will be derived based on the multiple imputed datasets for SALT I values using the same multiply imputed datasets than for sensitivity analysis #1 of primary efficacy endpoint (refer to Section 10.1). The same CMH test will then be performed and combined using Rubin's method. Combined proportion along with the 95% CI, and p-value will be reported.
- 2) **NRI in mFAS**: The main analysis of these secondary efficacy endpoints will be repeated based on the mFAS.
- 3) **NRI in PPS**: The main analysis of these secondary efficacy endpoints will be repeated based on the PPS.
- 4) **OC in FAS**: The proportion-based key secondary endpoints at Week 24 will be analyzed in FAS based on observed data without imputation.
- 5) **NRI in Randomized Set**: Missing proportion-based response status at Week 24 will be imputed as 'non-responders'. The same CMH test will then be performed in the

Randomized Set. The randomization stratification factor SALT I score (< 50 , $50 < 95$, ≥ 95) at Baseline will be used.

Subgroup Analyses

The same subgroup analyses as for the primary efficacy endpoint will be performed on all secondary endpoints descriptively using the FAS.

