11.6. Efficacy Analyses

The primary and secondary endpoints will be analyzed using the FAS. The exploratory endpoints will be analyzed using the FAS and the Randomized Set. Other important statistical

considerations, such as missing data imputation strategies, sensitivity analyses, and subgroup analyses will be described in the SAP.

The primary endpoint of percent change from Baseline to Week 24 in SALT I will be analyzed with a mixed-effects model repeated measures (MMRM) model. The MMRM model will include treatment group, visit, and interaction of treatment-by-visit as factors, and disease duration and Baseline SALT I score as covariates. An unstructured covariance matrix will be specified for the MMRM model. Least squares (LS) means at each visit and LS mean differences between treatment groups (each of the active arms versus placebo only) with p-values and corresponding 95% confidence intervals (CIs) will be reported. This method will also be applied to other score-based or continuous measures.

Proportion-based secondary endpoints at Week 24 will be analyzed using the Cochran-Mantel-Haenszel test method adjusted for the randomization stratification factor SALT I (< 50 , ≥ 50) at Baseline. Subjects with missing data for any reason will be considered as 'non-responder' or 'failure' for the endpoint. The number and percentage of subjects achieving the goal and the difference in proportion between treatment groups achieving the goal, along with p-values and the 95% CIs, will be reported.

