5.2 Adjustments for Covariates

For the continuous efficacy endpoints (e.g., change and percent change from baseline), disease duration and baseline value will be included as covariates in the statistical models, where disease duration, in years, will be calculated as follows:

$$\text{Disease duration (years)} = (\text{Randomization date} - \text{Initial onset date} + 1) / 365.25$$

Should the day be missing for the initial onset date, it will be imputed to the 1st of the month. Should both the day and month be missing for the initial onset date, they will be imputed to January 1st. Completely missing initial onset date will not be imputed.

For binary efficacy endpoints, Cochran-Mantel-Haenszel (CMH) tests will be stratified by the stratification factor for SALT I based on the value used by the IWRS at the time of randomization. If there are more than 10% of subjects who were mis-stratified, a sensitivity analysis will be conducted using the value from the clinical database.

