5.6 Multiple Comparisons/Multiplicity

No formal testing strategy or adjustments of the Type I error will be employed for the primary and secondary efficacy endpoints. Estimates and two-sided 95% Confidence Intervals (CIs) for treatment groups and from treatment comparisons will be reported in an exploratory manner.

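### The responder endpoints set a CMH p-value stratified by SALT I beside an unstratified difference and exact interval, so case mix enters the reported difference and the p-value and interval can disagree

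*SAP*

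**What the plan says.** SAP 10.2 (Main Analysis) covers the ≥30%, ≥50% and ≥75% improvement endpoints at Week 24. On the estimate it says: "The differences in proportion between each etrasimod treatment group and placebo, along associated two-sided 95% unconditional exact CIs, and p-value will also be reported". On the test, it says that each active group against placebo "will be analyzed using a CMH test, adjusted for the randomization stratification factor SALT I score", with the cut at 50. All Cohort 1 subjects are placed in the ≥50 stratum. SAP 5.2 confirms that "Cochran-Mantel-Haenszel (CMH) tests will be stratified by the stratification factor for SALT I based on the value used by the IWRS".

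Protocol 11.6 has these endpoints "analyzed using the Cochran-Mantel-Haenszel test method adjusted for the randomization stratification factor SALT I" and asks for the difference with p-values and 95% intervals. It names no interval method, so it does not require the pairing that the SAP chose.

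Neither document gives a stratified estimate of the difference, stratum weights or a stratified interval, or says which statistic the exact interval inverts. SAP 10.3 and 10.4 apply the same method to the exploratory and other proportion endpoints. On status, SAP 5.6 says: "Estimates and two-sided 95% Confidence Intervals (CIs) for treatment groups and from treatment comparisons will be reported in an exploratory manner".

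**The concern.** The p-value compares arms within SALT I strata. An unconditional exact interval for a risk difference is ordinarily built on one 2×2 table of two binomials, and the SAP gives nothing to stratify it with. The SAP does not use the word crude; that reading follows from the method and from the absence of strata or weights.

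Two consequences follow. First, the number printed beside the p-value is not the quantity tested. Cohort 1 adds only 2 mg and placebo subjects, all in ≥50, so after pooling the placebo arm holds relatively more severe subjects than the 3 mg arm, and the 2 mg arm more still. If response depends on baseline severity, the crude difference moves without any drug effect, in opposite directions for the two doses. Second, an asymptotic stratified test and an exact unstratified interval can fall on opposite sides of zero. A reader comparing doses in a Phase 2 trial would use the difference and its interval.

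**Working it through.** **Inputs from the documents.** Cohort 1: about 24 on 2 mg and 12 on placebo. Cohort 2: about 24 on 3 mg, 6 on 2 mg and 12 on placebo (SAP 3.2). Cohort 1 entry required SALT I ≥50 (Protocol 10.3.1). The FAS requires SALT I <95 (SAP 5.1).

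**Assumed, because the documents do not give them.** Response rates by stratum, the share of Cohort 2 in <50, and the number of Cohort 1 subjects in the FAS.

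**The plan's own figure.** The only power statement concerns the primary endpoint. It reproduces with a two-sample t-test (79.97% for 20 vs 10; 47.6% for 5 vs 10). No response rate or power is stated for the binary endpoints.

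**Step 1: shift in the crude difference with no drug effect.** With the same within-stratum rates in both arms, the expected crude difference is (share of active arm in <50 − share of placebo in <50) × (rate in <50 − rate in ≥50). The Mantel-Haenszel (MH) difference is 0.

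For 3 mg vs placebo, assume 10 of 24 and 5 of 20 in <50 (8 of the 20 placebo subjects from Cohort 1). The share gap is 0.417 − 0.250 = 0.167.

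| Assumed response, <50 / ≥50 | Shift, points |
|---|---|
| 10% / 5% | 0.167 × 5 = +0.8 |
| 20% / 5% | 0.167 × 15 = +2.5 |
| 30% / 10% | 0.167 × 20 = +3.3 |
| 40% / 10% | 0.167 × 30 = +5.0 |

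For 2 mg vs placebo, assume half of Cohort 2 is in <50, with 16 Cohort 1 subjects on 2 mg and 8 on placebo in the FAS. The shares are 3/22 = 0.136 and 6/20 = 0.300. At 40%/10% the shift is −0.164 × 30 = −4.9 points.

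**Step 2: p-value and interval can disagree in both directions.** CMH is taken with 1 df and no continuity correction. The exact interval excludes 0 when the one-sided exact tail, maximised over the common rate, is at most 0.025.

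*(a) 3 mg 6/12 (<50) and 4/12 (≥50); placebo 1/6 and 0/6.*
- Observed minus expected: 10 − (4.667 + 2.667) = 2.667. Variance: 1.007 + 0.732 = 1.739. CMH = 7.111/1.739 = 4.09, p = 0.043.
- Crude 10/24 vs 1/12, difference 33.3 points. The exact tail is 0.038 with either statistic, so the interval contains 0: −3.3 to 65.1 (raw difference) or −1.7 to 57.6 (score).
- The stratified difference is also 33.3 points. This conflict comes from setting an asymptotic test beside a conservative exact interval.

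*(b) 3 mg 8/12 and 3/12; placebo 3/6 and 0/18 (all 12 Cohort 1 placebo subjects in the FAS).*
- Observed minus expected: 11 − (7.333 + 1.2) = 2.467. Variance: 1.007 + 0.670 = 1.677. CMH = 6.084/1.677 = 3.63, p = 0.057.
- Crude 11/24 vs 3/24, difference 33.3 points. Tails are 0.015 (raw) and 0.007 (score), so the interval excludes 0: 3.2 to 59.2 or 6.6 to 56.7.
- MH weights nm/N are 4 and 7.2. The stratified difference is (4 × 0.167 + 7.2 × 0.250)/11.2 = 22.0 points. Here the estimand itself differs.

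**Step 3: how often.** Exact enumeration with 24 on 3 mg, 12, 18 or 24 on placebo, placebo rates of 5–40% and active rates of 5–70% gave disagreement in 0.6% to 19.3% of trials, depending on the setting and the statistic inverted.

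**Step 4: an interval that matches the test.** In each stratum, with n active, m placebo, N = n + m and t responders, the MH-weighted difference contributes (nm/N)(x/n − y/m) = x − nt/N, the CMH numerator. Under zero difference the Miettinen-Nurminen variance with the N/(N−1) factor is (nm/N)² × (t/N)(1 − t/N)(1/n + 1/m) × N/(N−1) = nm·t(N−t)/[N²(N−1)], the CMH variance. The squared statistic at zero is therefore the CMH chi-square. Numerically, (a) gives 33.3 points (1.2 to 56.3) with p = 0.043, and (b) gives 22.0 points (−0.7 to 46.5) with p = 0.057.

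**The case against.** The case for leaving the plan alone has substance. No decision rule uses these p-values or intervals, and there is no Type I error control. An exact interval with guaranteed coverage is defensible at about 20 per arm. SAP 5.7 already plans responder summaries by cohort and by SALT I (<50, ≥50), so a reader can see the case mix. Response of 30–40% in <50 without drug effect is hard to square with an entry requirement of stable disease, above all for the ≥50% and ≥75% endpoints.

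Most of this limits the size of the point without removing it. The subgroup tables are descriptive and supply no adjusted difference. For the continuous endpoints, SAP 10.1 adds models adjusted for SALT I stratum and cohort and a Cohort 2-only analysis; the binary sensitivity analyses in SAP 10.2 contain neither.

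A reader might go further and infer that contradictions will be common, for example about 22% of trials. That figure, from a simulation with placebo response of 10%/5% and a 25-point effect, needs the exact interval to invert the raw difference, which the SAP does not say. Single tables show the dependence. For 8/24 vs 1/20 (unstratified p = 0.022) the tail is 0.033 raw but 0.014 with the score statistic. For 6/24 vs 0/20 (p = 0.017) it is 0.052 raw but 0.009 score. With the score statistic both conflicts vanish. At the placebo rates behind the simulated 11–22%, the case-mix shift is only 0.8 to 2.5 points, so the largest disagreement rates there and the largest shifts do not belong to the same assumptions.

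**Conclusion.** The point holds as a mismatch between test and estimate in the secondary responder endpoints and in the exploratory and other proportion endpoints that follow SAP 10.2. The reported difference is not adjusted for the factor used in the test, and pooling Cohort 1 pushes it up for 3 mg and down for 2 mg when response is higher in <50. Under the stated assumptions the shift is about +1 to +5 points for 3 mg and about −5 points for 2 mg at the top of that range. Disagreement about zero ranges from rare to about one trial in five, and no single rate can be claimed. Within Cohort 2 alone, with balanced strata, the crude and stratified differences agree in expectation, and mainly the asymptotic-versus-exact conflict remains.

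The documents do not support reading SAP 5.6 as making these intervals the trial's main product: it calls estimates and intervals exploratory. The primary endpoint is untouched. The change is worth making because it is cheap and uses strata that the trial already has.

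**What to change.** In SAP 10.2, make the main estimate the Mantel-Haenszel stratified risk difference, with a stratified Miettinen-Nurminen score 95% interval using Mantel-Haenszel weights in the same strata as the CMH test. State the N/(N−1) factor, so that interval and p-value agree at zero. Keep the crude difference with the unconditional exact interval as supportive, label it unadjusted, and name the score statistic as the one inverted. Carry the change to the proportion endpoints in SAP 10.3 and 10.4.

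Name the method precisely, because other stratified intervals do not cure the disagreement. A Mantel-Haenszel interval with Sato variance disagreed with CMH in 2.4% to 14.4% of trials across three settings. A summary-score interval contradicted CMH in both worked tables (−2.6 to 52.2 for (a), 4.0 to 46.9 for (b)).

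The cost is SAP wording and one programming change. The downside is small: coverage of the main interval becomes approximate, and the supportive exact interval keeps the guaranteed one on view.

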10.3 Exploratory Efficacy Endpoints

SALT I

SALT I (refer to Section 10.1) will also be analyzed as follows:

- Percent change from Baseline in SALT I over time
- Change from Baseline in SALT I over time
- Proportion of subjects achieving a $\geq 30\%$ improvement from Baseline in SALT I over time
- Proportion of subjects achieving a $\geq 50\%$ improvement from Baseline in SALT I over time
- Proportion of subjects achieving a $\geq 75\%$ improvement from Baseline in SALT I over time
- Proportion of subjects achieving a $\geq 90\%$ improvement from Baseline in SALT I at Week 24
- Percent change from Baseline in SALT I at Week 24 as assessed by blinded central review
- Change from Baseline in SALT I at Week 24 as assessed by blinded central review
- Proportion of subjects achieving a $\geq 30\%$ improvement from Baseline in SALT I at Week 24 as assessed by blinded central review
- Proportion of subjects achieving a $\geq 50\%$ improvement from Baseline in SALT I at Week 24 as assessed by blinded central review
- Proportion of subjects achieving a $\geq 75\%$ improvement from Baseline in SALT I at Week 24 as assessed by blinded central review
- Proportion of subjects achieving a $\geq 90\%$ improvement from Baseline in SALT I at Week 24 as assessed by blinded central review

AASIS

The AASIS is a 13-item, disease-specific measure that asks participants about symptoms related to AA and how these symptoms interfere with daily functioning. Subjects will be asked to rate

how severe each of the following 7 symptoms pertaining to AA symptoms have been in the past week using an 11-point scale ranging from 0 “not present” to 10 “as bad as you can imagine”:

- Scalp hair loss
- Body or eye lashes hair loss
- Tingling/numbness of the scalp
- Itchy or painful skin
- Irritated skin
- Feeling anxious or worry
- Feeling sad

Subjects will also be asked to rate how severe each of the following 6 areas of daily functioning are interfered with by AA in the past week using an 11-point scale ranging from 0 = “did not interfere” to 10 “interfered completely”: work, enjoyment of life, interaction with others, daily activities, sexual relationships, and quality of life. The overall scoring system ranges from 0 to 10 (overall score is the arithmetic mean) with high scores indicative of greater AA symptom impact.

AASIS Symptoms Sub-score (1-7): If at least 4 out of 7 symptom items i.e., AASIS (1-7) questions have been answered, then AASIS symptoms sub-score will be the arithmetic mean of all answered symptom items; otherwise, the sub-score will be set to missing.

AASIS Interference Sub-score (8-13): If at least 3 out of 6 interference items i.e., AASIS (8-13) questions have been answered, then AASIS interference sub-score will be the arithmetic mean of all answered interference items; otherwise, the sub-score will be set to missing.

AASIS Total Score: If both AASIS Symptoms Sub-score (1-7) and AASIS Interference Sub-score (8-13) are not missing, then AASIS total score will be the arithmetic mean of all answered symptoms and interference items, otherwise the total score will be set to missing.

AASIS exploratory efficacy endpoint is:

- Change from Baseline in AASIS at Week 24

AA-QLI

The AA-QLI is a disease-specific questionnaire developed to evaluate the impact of AA on quality of life. The AA-QLI has been validated with the Dermatology Life Quality Index and shown to provide more comprehensive insights about psychological distress among AA patients specifically. The AA-QLI consists of 21 questions covering 3 areas of daily life: subjective symptoms, relationships, and objective signs. AA-QLI Total Score is derived as the sum of the scores for the 21 questions. The results are presented on a scale varying between 21 and 84; a score

of 21 represents the best quality of life, while a score of 84 represents the poorest quality of life outcomes. AA-QLI Total Score will be set to missing if at least one question is not answered.

AA-QLI exploratory efficacy endpoint is:

- Change from Baseline in AA-QLI at Week 24

Lymphocyte Counts and Infections

Clinical safety laboratory tests will be completed predose at each study visit.

Lymphocyte counts exploratory efficacy endpoint is:

- Percent change from Baseline in peripheral lymphocyte counts at Week 24

Exploratory Endpoint Analyses

Main Analysis

With the following exception, exploratory efficacy endpoints will be summarized and analyzed as for the main analysis of the secondary efficacy endpoints (refer to Section 10.2).

The exception is that the change and percent change from Baseline in SALT I at Week 24 as assessed by blinded central review will be summarized as the primary efficacy endpoint (refer to Section 10.1), but analyzed using an ANCOVA model based on observed-cases (missing data will not be imputed) and including treatment group as fixed effect, and disease duration (years) and Baseline SALT I score as covariates. LS means and LS mean difference between each etrasimod treatment group and placebo will be reported along with two-sided 95% CI and p-value.

Sensitivity Analyses

No sensitivity analyses will be performed for the exploratory efficacy endpoints.

Subgroup Analyses

The same subgroup analyses as for the primary efficacy endpoint will be performed for the exploratory efficacy endpoint of percent change from Baseline in peripheral lymphocyte counts at Week 24.

No subgroup analyses will be performed for other exploratory efficacy endpoints.

10.4 Other Efficacy Endpoints

The following other efficacy endpoints will also be summarized and analyzed:

- Proportion of subjects achieving a SALT I score ≤ 10 over time
- Proportion of subjects achieving a SALT I score ≤ 20 over time

- Proportion of subjects achieving a $\geq 90\%$ improvement from Baseline in SALT I over time
- Change from Baseline in AASIS at Week 12
- Change from Baseline in AA-QLI at Week 12
- Percent change from Baseline in peripheral lymphocyte counts at Weeks 1 (Cohort 2 only), 2, 4, 8, 12, 16, and 20

Other efficacy endpoints will be summarized and analyzed as for the proportion-based exploratory efficacy endpoints or continuous exploratory efficacy endpoints, as applicable, for visits occurring during the DB Treatment Period (refer to Section 10.3).

No sensitivity analyses and no subgroup analyses will be performed for the other efficacy endpoints.

10.5 Exploratory Efficacy Endpoints during the Open-Label Extension Period

The following efficacy endpoints will be assessed at scheduled visits during the OLE Period up to 52 weeks:

- Change and percent change from Baseline in SALT I over time
- Change from Baseline in AASIS over time
- Change from Baseline in AA-QLI over time
- Change from Baseline in peripheral lymphocyte counts over time
- Proportion of subjects achieving a $\geq 30\%$ improvement from Baseline in SALT I over time
- Proportion of subjects achieving a $\geq 50\%$ improvement from Baseline in SALT I over time
- Proportion of subjects achieving a $\geq 75\%$ improvement from Baseline in SALT I over time
- Proportion of subjects achieving a $\geq 90\%$ improvement from Baseline in SALT I over time
- Proportion of subjects achieving a SALT I score ≤ 10 over time
- Proportion of subjects achieving a SALT I score ≤ 20 over time

These endpoints will be summarized by visit using descriptive statistics based on the OLE FAS, with following considerations:

- Missing data will not be imputed

- Summaries will be provided for the three treatment groups in the OLE Period (OLE 2mg, OLE 2mg/3mg, OLE 3mg) and three randomized treatment groups in the DB Treatment Period (DB 2mg, DB 3mg, DB placebo)
- Change and percent change from baseline in continuous variables will be summarized using change from OLE Baseline and DB Baseline (refer to Section 4.1).

The photographic assessments of the full scalp for all subjects, of the eyebrows and eyelashes for subjects who have hair loss in these areas at Day 1/Baseline, and of the fingernails for subjects with fingernail changes related to AA (eg, pitting, white spots, and roughness) at Day 1/Baseline, will be reported in listing.

10.6 Summary of Efficacy Analyses

Table 3. Summary of Efficacy Analyses

Efficacy Endpoint	Primary/Main Analysis	Sensitivity Analysis
DB Treatment Period		
Primary		
Percent change from baseline in SALT I	FAS, OC (MMRM)	#1 FAS, MI (ANCOVA) #2 mFAS, OC (MMRM) #3 PPS, OC (MMRM) #4 Randomized Set, OC (MMRM) #5 FAS, OC (MMRM), adjusting for the SALT I stratification variable and cohort #6 FAS, OC (MMRM), including Cohort 2 only and adjusting for the SALT I stratification variable #7 FAS, OC (MMRM), excluding Etrasimod 3 mg and adjusting for the SALT I stratification variable and cohort
Secondary		
Change from baseline in SALT I	FAS, OC (MMRM)	#1 FAS, MI (ANCOVA) #2 mFAS, OC (MMRM) #3 PPS, OC (MMRM) #4 Randomized Set, OC (MMRM) #5 FAS, OC (MMRM), adjusting for the

Efficacy Endpoint	Primary/Main Analysis	Sensitivity Analysis
		SALT I stratification variable and cohort #6 FAS, OC (MMRM), including Cohort 2 only and adjusting for the SALT I stratification variable #7 FAS, OC (MMRM), excluding Etrasimod 3 mg and adjusting for the SALT I stratification variable and cohort
Binary secondary endpoints in SALT I	FAS, NRI (CMH)	#1 FAS, MI (CMH), #2 mFAS, NRI (CMH) #3 PPS, NRI (CMH) #4 FAS, OC (CMH) #5 Randomized Set, NRI (CMH)
Exploratory		
Change and percent change from Baseline in SALT I over time Change from Baseline in AASIS at Week 24 Change from Baseline in AA-QLI at Week 24 Percent change from baseline in peripheral lymphocyte counts at Week 24	FAS, OC (MMRM)	
Binary exploratory endpoints in SALT I over time	FAS, NRI (CMH)	
Change and percent change from Baseline in SALT I by blinded	FAS, OC (ANCOVA)	

Efficacy Endpoint	Primary/Main Analysis	Sensitivity Analysis
central review at Week 24		
Binary exploratory endpoints in SALT I by blinded central review at Week 24	FAS, NRI (CMH)	
Other		
Binary other endpoints in SALT I over time	FAS, NRI (CMH)	
Change from Baseline in AASIS at Week 12 Change from Baseline in AA-QLI at Week 12 Percent change from baseline in peripheral lymphocyte counts over time	FAS, OC (MMRM)	
OLE Period		
Change and percent change from DB and OLE Baseline in SALT I over time Change from DB and OLE Baseline in AASIS over time Change from DB and OLE Baseline in AA-QLI over time	OLE FAS, OC (Descriptive)	

Efficacy Endpoint	Primary/Main Analysis	Sensitivity Analysis
Change from DB and OLE Baseline in peripheral lymphocyte counts over time		
Proportion-based exploratory endpoints in SALT I over time	#1: OLE FAS, OC (Descriptive) #2: OLE FAS, NRI (Descriptive)	

